## BACKGROUND

Elder mistreatment (EM) is estimated to affect 1 in 10 older adults (60+) in the US2 (5,600,000 victims nationwide). In NY State, the Elder Abuse Prevalence Study found that 141 out of 1000 older adults experienced mistreatment since turning 60. Mistreatment victims have high rates of depressive symptoms: Victims of EM have one of the highest rates of depression among older adults (<http://www.aoa.acl.gov/>). A population-based study found that mistreatment victims had significantly higher rates of depressive symptoms (31.6% vs. 6.8%) and suicidal ideation (16.4% vs. 3.4%) than non-mistreated older adults. In our own work in NYC, 34% of victims endorsed significant depressive symptoms (PHQ-9 $\geq$ 10) and 16% reported suicidal ideation. EM/ PROTECT recognizes that resignation of depression acts a barrier to the use of EM services. Thus, mistreatment resolution services alone, while necessary, may be insufficient. Similarly, treatment of depression alone may be insufficient when victims continue to be exposed to the chronic stress of mistreatment. For this reason, EM/PROTECT acts in synergy with mistreatment resolution services. In EM/PROTECT, staff of EM services staff offer mistreatment resolution services. EM/PROTECT is neurobiologically informed and simplified to fit within EM agencies. Consistent with our Center's deployment focused model, EM/PROTECT has been developed through an iterative process with the NY City Elderly Crime Victim Resource Center (ECVRC). EM aims to install protection measures, while PROTECT targets the behavioral consequences of stress on the CCN and the reward networks thus reducing the experience of stress. Accordingly, PROTECT therapists work with victims to implement action plans promoting self-protective behaviors and expanding their meaningful rewarding activities.

## STUDY DESIGN

Aims: Due to the limited recruitment time available (the study ends on 8/31/21), we propose to offer Virtual PROTECT (video preferred) to all subjects (N=40) and test the acceptability of Virtual PROTECT by depressed victims of mistreatment abuse and by community clinicians. Our early experience during the COVID-19 crisis, suggests that it is possible to deliver therapy via video or telephone to this vulnerable population. Accordingly, the Primary Aim of this study is to test the acceptability of Virtual PROTECT by depressed victims of mistreatment and by community-based clinicians (licensed clinical social workers, LCSW). A secondary aim of the study is to examine whether Virtual PROTECT is more effective than in-person EM/PROTECT in reducing symptoms of depression and in improving quality of life. We expect that participants receiving Virtual PROTECT will have an even greater decrease in depressive symptoms than a historical comparison group (N=24) who received EM/PROTECT in person because of the enhanced strategies for "reward exposure" and the introduction of behavioral economics incentives for pursuing rewarding activities. EM/PROTECT did not improve quality of life more to EM/MH (elder mistreatment services plus mental health referral). The reasons may be that quality of life in depressed victims of mistreatment abuse is influenced by more factors than severity of depression. We will examine, however, if Virtual PROTECT will improve quality of life more than EM/PROTECT because of the enhanced "reward exposure" strategies and the adherence incentives of behavioral economics.

### Primary Hypotheses:

- H1) More than 75% of Virtual PROTECT will attend each scheduled session.
- H2) Victims will have an average satisfaction (CSQ) score greater than 3 (out of 4) at 3, 6, and 12 weeks follow-up.
- H3) Community clinicians (LCSW) will have an average satisfaction (CSQ) score greater than 3 (out of 4) at the end of the project.

Secondary Hypotheses: Compared to EM/PROTECT (9 sessions, in-person), Virtual PROTECT participants will have: SH1) greater reduction (effect size) and clinically significant reduction in depression ( $\Delta$  MADRS  $\geq$ 3 pts by 12 weeks); SH2) improved quality of life (Primary Outcome:

WHOQOL-BRF).

In addition, to the above comparison, we will compare Virtual PROTECT with a historical comparison group (EM/MH, N=16) who received elder mistreatment services plus mental health referral as part of the first project.

**Power analysis:** The primary goal of this study is to establish the acceptability of Virtual PROTECT and obtain preliminary estimates of effect sizes for the improvement in depressive symptoms among Virtual PROTECT participants compared to PROTECT participants. Therefore, we estimated that with 40 Virtual-PROTECT participants, we will have a 95% confidence interval width of 24% for the acceptability (assuming a benchmark of 75%). With 40 Virtual PROTECT and 24 EM/PROTECT (in-person) participants, we can obtain an estimate of the difference in reduction of depression (MADRS) over the course of treatment between the two treatment groups with a 95% confidence interval half-width of 3.0 points. Therefore, we have adequate sample size to test our acceptability hypotheses and obtain a preliminary estimate of effect size with reasonable confidence in order to carry out an adequate powered trial.

**Aim 1. Finalize the Manual and Training:** We will finalize the EM/PROTECT Manual and use it to train Licensed Clinical Social Workers (LCSWs) at each EM agency. We will record the training hours needed to achieve certification in EM/PROTECT, the success rate of LCSWs in achieving certification and problems encountered during this process.

**Aim 2. PROTECT Operations Manual:** We will create an Operations Manual with the staff of EM agencies describing how PROTECT will be integrated into the agency, i.e. communication between EM staff, LCSWs, and research staff, PHQ-9 tracking and hand-off, and review of ongoing activities.

**Aim 3. Evaluate the reach, feasibility and acceptability:** 1) Reach: The number of clients screened vs. all eligible for screening, and the number clients referred who meet study criteria. 2) Feasibility: Number of victims who initiate EM/PROTECT or EM/MH (elder mistreatment services plus mental health referral) victims who make contact with mental health services and the number who attend research procedures. EM/PROTECT: session completion rate; smartphone use; 3) Acceptability: Victims satisfaction (CSQ)8 in both treatments; EM/PROTECT session completion at 6, 9, and 12 weeks. EM/PROTECT Benchmarks: More than 75% will attend each session. LCSWs staff satisfaction will be assessed throughout the study.

**Aim 4. Preliminary Effectiveness Pilot:** Primary H1 Compared to EM/MH, EM/PROTECT (9 sessions) participants will have greater (effect size) and clinically significant reductions in depression ( $\Delta$  MADRS  $\geq 3$  pts by 12 weeks); Primary H2 improved quality of life (Primary Outcome: WHOQOL-BRF). As both EM/MH and EM/PROTECT are active conditions we will examine within-treatment differences in outcomes.

**Aim 5. Target Engagement:** Secondary H (SH): The differential effect of EM/PROTECT vs. EM/MH in reducing depression over 12 weeks is mediated by changes in: Primary target stress change from baseline to 6 weeks on the Perceived Stress Scale. Secondary target exposure to meaningful, rewarding activities at 6 weeks [Primary Measure: Behavioral Activation Scale (BADS)].

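### The stated 95% confidence interval width of 24% for acceptability does not follow from 40 participants and a 75% benchmark; those inputs give about 27%

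*Combined protocol and SAP*

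**What the plan says.** The Study Design section sets the size of the single prospective group: "we propose to offer Virtual PROTECT (video preferred) to all subjects (N=40"). The acceptability of Virtual PROTECT is the primary aim, and the first primary hypothesis is a proportion: "More than 75% of Virtual PROTECT will attend each scheduled session".

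The power analysis paragraph, placed under the Primary Hypotheses heading, begins its precision statement with "we estimated that with 40 Virtual-PROTECT participants" and continues "we will have a 95% confidence interval width of 24% for the acceptability (assuming a benchmark of 75" per cent). The next sentence gives a precision for the secondary comparison with the historical in-person group: a half-width of 3.0 MADRS points. The paragraph then concludes: "Therefore, we have adequate sample size to test our acceptability hypotheses".

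The paragraph does not name an interval method, give a second assumed proportion, or allow for dropout or missing attendance data.

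**The concern.** The sentence contains everything needed to check it: the sample size, the confidence level, the assumed proportion and the resulting width. The four values do not fit together, because 40 participants at 75% cannot give an interval as narrow as 24 points at the 95% level.

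The 24% is the only planning figure for the primary aim; the other precision figure in the paragraph belongs to a secondary comparison. A reader who takes it at face value will expect a tighter estimate of attendance than the design can give, and will read the adequacy statement as resting partly on that precision.

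**Working it through.** **Inputs, all from the power analysis paragraph**
- n = 40 (also given in the opening paragraph of Study Design)
- confidence level 95%, so z = 1.96
- assumed proportion p = 0.75 ("assuming a benchmark of 75" per cent)
- stated result: width 24%

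I read the width as the full width, upper limit minus lower limit, because the next sentence uses the word half-width when it means half-width.

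**Step 1. Try to reproduce the plan's figure (Wald interval)**

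Full width = 2 × z × √(p(1 − p)/n)

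= 2 × 1.96 × √(0.75 × 0.25/40) = 3.92 × √0.0046875 = 3.92 × 0.06847 = 0.268

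The result is 26.8 points (half-width 13.4; interval 61.6% to 88.4%). The plan's 24% is not reproduced.

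**Step 2. Try other 95% methods at 30/40**

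| Method | Full width (points) |
|---|---|
| Wilson | 26.0 (59.8% to 85.8%) |
| Jeffreys | 26.2 |
| Agresti-Coull | 26.3 |
| Arcsine | 26.4 |
| Logit | 26.5 |
| Wald | 26.8 (61.6% to 88.4%) |
| Wald with t quantile | 27.7 |
| Wilson, continuity-corrected | 28.3 |
| Clopper-Pearson (exact) | 28.5 (58.8% to 87.3%) |
| Wald, continuity-corrected | 29.3 |

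The smallest is 26.0, so rounding does not explain 24. From Wilson to exact, the interval is 8% to 19% wider than stated (26.0/24 = 1.08; 28.5/24 = 1.19).

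**Step 3. Ask which inputs would give 24%**

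- *Sample size.* n = 4z²p(1 − p)/w² = 3.92² × 0.1875/0.24² = 50.0 by Wald (50.02 unrounded; n = 50 gives 24.0 points). For a width of 24 points or less, Wilson needs 48, Agresti-Coull and Jeffreys 49, and exact 56. If any width that rounds to 24 is accepted (24.5 or less), the requirement is still 46 (Wilson) to 54 (exact), with Wald at 48.
- *Proportion.* Wald at n = 40 needs p(1 − p) = 40 × (0.12/1.96)² = 0.150, so p = 0.816. Wilson at 32/40 (80%) gives 24.3, and exact at 34/40 (85%) gives 24.1.
- *Confidence level.* A Wald width of 24 points at n = 40 and p = 0.75 corresponds to about 92% confidence. At 90%, Wald gives 22.5 and exact 24.5.
- *Half-width reading.* A half-width of 24 points needs n = 1.96² × 0.1875/0.24² = 12.5, about 13 participants, so this reading fails too.

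Each route to 24% requires changing at least one value that the paragraph states.

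**The case against.** The strongest reply accepts the arithmetic and disputes its importance.

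- **Size.** The Wald discrepancy is 26.8 − 24 = 2.8 points of full width, or 1.4 points each side; under Wilson it is 1.0 each side.
- **No threshold is crossed.** The plan sets no target width that 24% meets and 27% misses. The adequacy statement follows two precision figures, not one, and the opening of Study Design attributes the single-group design to limited recruitment time.
- **Limited reach.** The attendance hypothesis is stated as a benchmark, with no rule tied to an interval bound. The other two primary hypotheses are mean satisfaction scores, to which this width does not apply.
- **Unknown cause.** The hypothesis expects attendance above 75%. At 80% the Wilson width is 24.3, which rounds to 24, so the fault may lie in the stated proportion and not in the width.
- **N = 50 is one method's answer.** The plan names no method, and the range is 48 to 56.

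Most of this stands as a limit on the consequences. The practical gap is small, no conclusion is shown to reverse, and the required N should be given as a range. It does not rescue the sentence. The plan states 75% and no other proportion, and at 75% every method tried gives more than 24%. The possibility of a misstated proportion widens the choice of correction but does not remove the need for one.

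**Conclusion.** The point holds. With the inputs the plan states, the full width of the 95% interval is 26.8 points by Wald, 26.0 by Wilson and 28.5 by the exact method, against the stated 24. The error is in the favourable direction under all ten methods tried. The stated precision corresponds to about 50 participants by Wald, 25% more than the 40 planned (50/40 = 1.25), or 48 to 56 depending on method.

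This rests on reading width as full width and on all 40 participants contributing attendance data. With no allowance for dropout, missing data would widen the interval further at the same proportion.

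The sentence needs correcting because it is the sole precision figure for the primary aim and leads into an adequacy claim. The practical effect is modest: it neither biases an analysis nor makes the pilot infeasible. The documents do not show where 24% came from.

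**What to change.** Replace the sentence in the power analysis paragraph with, for example: *With 40 Virtual PROTECT participants, the 95% confidence interval for an attendance rate of 75% has a full width of about 27 percentage points (Wald; 62% to 88%).* If another method is intended, use its figure: 26 points for Wilson or 28.5 for exact. In either case name the method, so that the planned precision and the reported interval match.

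If 24% was derived from a different proportion or method, state those inputs in place of the 75% and show that they give 24%.

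Reread the adequacy sentence against the corrected figure. The cost is one sentence of protocol text and a slightly less favourable stated precision. The sample size, hypotheses and procedures do not change.

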## INCLUSION AND EXCLUSION CRITERIA

### Inclusion Criteria:

- 55 years of age or older
- Capacity to consent (per Elder Mistreatment staff)
- Significant depression (per Elder Mistreatment staff) as indicated by a score of 10 or above on the Patient Health Questionnaire-9 (PHQ-9), a widely used screening tool routinely administered in Elder Mistreatment (EM) agency settings (the PHQ-9 has a sensitivity of 88% and a specificity of 88% for major depression)
- Need for EM services

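### Aim 4 hypothesises a greater MADRS reduction with EM/PROTECT than with EM/MH, but the only analysis it names is within-treatment differences

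*Combined protocol and SAP*

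**What the plan says.** All references are to the Combined protocol and SAP, STUDY DESIGN, unless another section is named.

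- **Aim 4, hypothesis.** It is comparative: "Primary H1 Compared to EM/MH, EM/PROTECT (9 sessions) participants will have greater (effect size"), with a MADRS change of at least 3 points by 12 weeks given as the mark of clinical significance. Quality of life (WHOQOL) is the second outcome.
- **Aim 4, analysis.** One sentence follows: "As both EM/MH and EM/PROTECT are active conditions we will examine within-treatment differences in outcomes". No test, model, estimate or interval is given for EM/PROTECT minus EM/MH.
- **Aim 5.** The mediation hypothesis takes as its starting point "The differential effect of EM/PROTECT vs. EM/MH in reducing depression over 12 weeks", which is a between-group effect. No model is named.
- **Aims paragraph.** A comparative result is already reported for the other outcome: "EM/PROTECT did not improve quality of life more to EM/MH". No corresponding MADRS result is given.
- **Secondary Hypotheses.** The 16 EM/MH participants are described as people "who received elder mistreatment services plus mental health referral as part of the first project". In the current study every new participant receives Virtual PROTECT.
- **Power analysis.** For Virtual versus in-person PROTECT, the target is stated as the "difference in reduction of depression (MADRS) over the course of treatment between the two treatment groups", with a 95% CI half-width of 3.0 points. That is a different pair of groups.

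**The concern.** The hypothesis in Aim 4 is about a difference between two groups. The analysis it names, followed literally, gives two separate changes and does not estimate that difference.

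The reason offered is that both conditions are active. An active comparator may make the difference smaller and harder to detect, but the question is still between-group.

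A fall within one arm combines the effect of treatment, the natural course of depression and regression to the mean. The last is to be expected because entry is selected on a high score, "as indicated by a score of 10 or above on the Patient Health Questionnaire-9 (PHQ-9"). BACKGROUND indicates how selective that cut-off is: "In our own work in NYC, 34% of victims endorsed significant depressive symptoms" at that level.

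At stake is whether a reader gets an estimate with a confidence interval for the hypothesised difference, and whether Aim 5 has a defined effect to mediate.

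**Working it through.** **1. The plan's own figure.** Aim 4 states no sample size or precision for EM/PROTECT versus EM/MH. The nearest figure is the 3.0-point half-width for 40 versus 24. No MADRS SD is given, so it cannot be reproduced, only solved backwards. Assuming an unadjusted comparison of change scores:

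SD of change = 3.0 / (1.96 × √(1/40 + 1/24)) = 3.0 / (1.96 × 0.2582) = 5.93.

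This SD is carried forward as an assumption.

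**2. Precision of the missing contrast, unadjusted.** Group sizes are 24 (EM/PROTECT) and 16 (EM/MH), from the Aims paragraph and Secondary Hypotheses.

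Half-width = 1.96 × SD × √(1/24 + 1/16) = 1.96 × SD × 0.3227.

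| SD of change | Half-width (MADRS points) |
|---|---|
| 4 | 2.53 |
| 5.93 | 3.75 (3.87 using t with 38 df) |
| 8 | 5.06 |

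At SD 5.93, an observed difference of 3 points would have an interval of 3 ± 3.75, that is −0.75 to 6.75.

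**3. Precision after baseline adjustment.** With equal variance at baseline and 12 weeks and correlation r between them (assumed), the half-width is multiplied by √((1 + r)/2):

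- r = 0.3: 3.75 × 0.806 = 3.02
- r = 0.5: 3.75 × 0.866 = 3.25
- r = 0.7: 3.75 × 0.922 = 3.46

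**4. Regression to the mean within one arm.** From the documents: 34% of victims reach a PHQ-9 of 10 or above. Under a normal model, keeping the top 34% means z = 0.412. Their mean PHQ-9 then lies φ(z)/0.34 = 1.078 SD above that of all victims.

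Assumed, because not given: the MADRS SD among all victims, and the amount by which the screening PHQ-9 correlates less with 12-week MADRS than with baseline MADRS.

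Expected fall with no treatment effect = 1.078 × SD × drop in correlation.

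| MADRS SD | Drop 0.1 | Drop 0.2 | Drop 0.3 |
|---|---|---|---|
| 6 | 0.65 | 1.29 | 1.94 |
| 8 | 0.86 | 1.72 | 2.59 |
| 10 | 1.08 | 2.16 | 3.23 |

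A simulation at SD 8 gave 0.85, 1.72 and 2.58. The fall passes 3 points only when both inputs are at the top of their ranges. If both arms entered under the same rule, which is assumed, this component cancels in the between-group difference. It does not cancel in either within-arm change.

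**The case against.** The strongest reply is that the sentence adds to the comparison and does not replace it. It follows a comparative hypothesis and does not say that within-treatment differences are all that will be examined. With an active comparator, a small difference can hide improvement in both arms, so looking at each arm as well is sensible. The quality-of-life result shows that the two groups were in fact compared on one outcome, and SH1 uses similar effect-size language that the Power analysis treats as a between-group difference. This stands in part: a reader might infer that the plan rules out or abandons the between-group comparison, and the documents do not support that. What remains is that no MADRS contrast for this pair is named or reported in the supplied text.

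A reader might also infer that EM/PROTECT would be declared better if its arm improved significantly and EM/MH did not. The plan states no such rule. Both changes would be visible and could be subtracted, so the loss is a stated estimate and interval, and no wrong conclusion follows automatically.

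Three further points stand:

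- The text does not say whether the 3 points are a within-arm change or a between-group difference. If the former, within-arm analysis does answer that part of the hypothesis.
- The regression-to-the-mean range rests on inputs outside the documents and applies 34% from the team's earlier work to this referral population.
- The comparison appears to be complete, and a first-project analysis plan, if there is one, is not in the supplied text.

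**Conclusion.** The concern holds, as a minor point. Aim 4 poses a between-group question on MADRS and names only within-treatment analysis. The stated reason does not justify omitting the contrast, and Aim 5 relies on an effect that the text never commits to estimating.

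The plausible size is a fall of 0.6 to 3.2 points per arm without any treatment effect, 1.7 at SD 8 and a correlation drop of 0.2. This is conditional on the normal model, the 34% figure applying here, and the assumed SD and correlations. It illustrates why within-arm change is not enough; it does not show that any result is wrong.

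The scope is the EM/PROTECT versus EM/MH comparison, apparently from the first project, and the mediation aim built on it. Because Aim 4 labels its hypotheses as primary, a reader might take this as a flaw in the current study's primary analysis. The documents do not support that: the current H1 to H3 concern attendance and satisfaction, and the Virtual versus in-person contrast is already framed as a between-group difference.

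**What to change.** Replace the analysis sentence in Aim 4 with: *EM/PROTECT vs EM/MH is assessed by the between-group difference in MADRS and WHOQOL change, adjusted for baseline, with a 95% CI; within-group changes are descriptive.* Use that MADRS contrast as the effect in Aim 5. As a separate editorial step, naming the Aim 5 model and marking the EM/PROTECT versus EM/MH hypotheses in Aims 3 to 5 as first-project aims would remove the overlap with the current primary hypotheses.

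The cost is one sentence of protocol text and a between-group model for each outcome on 40 participants whose data have apparently already been collected. There are three drawbacks to state openly:

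- **Imprecision.** The half-width is about 3.75 MADRS points unadjusted and about 3.0 to 3.5 adjusted, so it is no smaller than the 3-point threshold at the assumed SD. The result is preliminary.
- **Timing.** The model would be specified after the historical data were collected and the quality-of-life result was known, so it cannot count as pre-specified.
- **Comparability.** The supplied text does not describe how first-project participants were allocated. The contrast is free of confounding only if the two groups were comparable, and baseline adjustment alone does not guarantee that.

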## INCLUSION AND EXCLUSION CRITERIA

### Inclusion Criteria:

- 55 years of age or older
- Capacity to consent (per Elder Mistreatment staff)
- Significant depression (per Elder Mistreatment staff) as indicated by a score of 10 or above on the Patient Health Questionnaire-9 (PHQ-9), a widely used screening tool routinely administered in Elder Mistreatment (EM) agency settings (the PHQ-9 has a sensitivity of 88% and a specificity of 88% for major depression)
- Need for EM services

